11 STATISTICAL CONSIDERATIONS

11.1 Study Hypotheses

This is a cross-sectional questionnaire of Network dentists and dental therapists assessing their treatment practices regarding the management of deep carious lesions. As such, formal hypothesis testing will not be conducted to achieve the study objectives.

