11.2 Sample Size Considerations

The primary aim of the study is descriptive (i.e., to estimate the level of concordance with national guidelines in the sample overall as well as in selected subgroups). As such, sample size calculations are based on the precision with which we can estimate guideline concordance. To a good approximation, if W is the width of the 95% confidence interval (i.e., the confidence interval is of the form $P \pm W/2$) for an estimated proportion P based on N observations, then the N needed to achieve that width is given by

$$N = 16*P*(1-P) / (W^2)$$
,

where P and W are expressed on a fractional basis. Thus, a proportion of 20% corresponds to P=0.20, and if the width of the conf interval were 10 percentage points then W would be 0.10. For a given value of W, the formula above is symmetric about P=0.5 and is largest for P=0.5. Hence using P=0.5 above will give a conservative value of N that assures a width \leq W regardless of the value of P.

The target N of 385 chosen for this study will enable us to estimate proportions for the population as a whole with a precision (95% confidence interval) of no greater than \pm 5 percentage points, \pm 7.1 percentage points for subgroups of size N/2, \pm 8.7 percentage points for subgroups of size N/3, and \pm 10 percentage points for subgroups of size N/4.

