11.3 Final Analysis Plan

Primary Objective: Determine the extent to which, for permanent posterior teeth with deep occlusal caries extending to the inner 1/3 of dentin, Network dentists and dental therapists use caries removal strategies that are in concordance with the recommendations of the ICCC.

The primary analysis will be descriptive in nature. The source data for this analysis will be the proportion of the time dentists and dental therapists say they remove all caries at the periphery of the cavity and stop before the pulp is exposed ("selective caries removal"), which will be assessed separately for patients with symptomatic caries and for patients with asymptomatic caries. For each of these two subgroups, we will describe this as a continuous measure using either means and standard deviations (SD) or, if the data are markedly skewed, medians and interquartile ranges.

We will also calculate the percentage of dentists who are "concordant" with guidelines by dichotomizing this measure. Since there is no universally agreed upon definition for how to define concordance based on such data, we plan to use a variety of cut points to document the extent to which concordance varies with the choice of threshold used to define concordance. These cut points will range from a high of selective caries removal 75% of the time, which we feel is a reasonable measure of good concordance, to a low of selective caries removal 25% of the time to allow for comparison with some previous reports in the literature (15,21,22).

As a secondary analysis, we will use logistic regression analysis to determine the extent to which concordance varies according to selected provider characteristics. For the purposes of this analysis, we will define concordance using our upper end threshold of selective caries removal 75% of the time. We will initially look at all candidate variables in a univariate manner and will use those significant based on these analyses to conduct a reverse stepwise multiple logistic regression analysis. As before, separate analyses will be done for patients with symptomatic caries and for patients with asymptomatic caries.

An additional secondary analysis related to this objective will be to assess the relative importance of various factors when making clinical decisions about management of deep carious lesions. Each factor will be graded on a 5-point Likert scale and simple descriptive statistics will be used to summarize the information.

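### Section 11.3 selects provider correlates of concordance by univariate significance and reverse stepwise regression, which inflates the odds ratios that a stated estimation aim needs to be unbiased

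*Protocol*

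**What the plan says.** Section 11.3 of the protocol adds a secondary analysis under the primary objective. Logistic regression is to be used "to determine the extent to which concordance varies according to selected provider characteristics". The outcome is binary: "we will define concordance using our upper end threshold of selective caries removal 75% of the time".

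The model is built in two steps. All candidate variables are examined univariately, and the team "will use those significant based on these analyses to conduct a reverse stepwise multiple logistic regression analysis". The procedure is run twice, because "separate analyses will be done for patients with symptomatic caries and for patients with asymptomatic caries". No shrinkage, validation or other allowance for the selection is described.

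Two other passages bear on this:
- Section 11.1 states that "formal hypothesis testing will not be conducted to achieve the study objectives".
- Section 11.2 sets the sample size for the precision of a single proportion, not for a regression model: "The target N of 385 chosen for this study will enable us to estimate proportions for the population as a whole" to within 5 percentage points.

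**The concern.** The aim is to estimate the size of associations, but the method decides by p-value which associations are seen at all. With a few hundred respondents, a moderate association passes a significance filter mainly in those samples where chance has made it look larger. The ORs that survive are therefore too large on average, and ordinary CIs computed after selection take no account of this.

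Selection is also unstable. A real correlate can be kept for symptomatic caries and dropped for asymptomatic caries without any true difference between them. The protocol plans no formal comparison of the two models, but readers shown them together may take a different list of variables as a finding.

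Practice type defines the sampling strata (Sections 4 and 5.2), and under this rule it too can drop out of one or both models. At stake is the credibility of the list of characteristics associated with concordance and of the effect sizes attached to it.

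**Working it through.** **1. The plan's own figure.** With z = 1.96, P = 0.5 and W = 0.10, N = 4z²P(1−P)/W² = 4 × 3.8416 × 0.25 / 0.01 = 384.2, rounded up to 385. The half-width at 385 is 1.96 × √(0.25/385) = 0.0499. The protocol's 385 is reproduced. (The printed constant 16 is z = 2 rounded, gives 400, and is described there as an approximation.) So 385 is the N available to the regression.

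**2. Inputs the protocol does not give for this analysis.** These are the number of candidates, the significance level at each step, and the share concordant at the 75% threshold. Assumed: 10 or 15 candidates, 0.05 at both steps, and concordance of 12 to 50%.

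**3. Hand check of the mechanism.** Take one binary characteristic split evenly, with a true OR of 1.5 (log OR 0.405). The standard error of the log OR is about 1/√(385 × 0.25 × p(1−p)), where p is the share concordant. The estimate passes the 0.05 screen in the right direction only if it exceeds t = 1.96 × SE. Write a = (t − 0.405)/SE. The chance of passing is 1 − Φ(a), and the mean log OR among those passing is 0.405 + SE × φ(a)/(1 − Φ(a)).

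| p | Events (385 × p) | SE | Smallest OR that passes | Chance of passing | OR when it passes |
|---|---|---|---|---|---|
| 12% | 46 | 0.314 | 1.85 | 25% | 2.23 |
| 20% | 77 | 0.255 | 1.65 | 36% | 1.96 |
| 25% | 96 | 0.235 | 1.59 | 41% | 1.88 |
| 50% | 192 | 0.204 | 1.49 | 51% | 1.76 |

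At 12 to 25% concordance, a true OR of 1.5 can be selected only when it is overestimated.

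**4. Simulation of the full two-step procedure at N = 385.**
- *One true OR of 1.5 among 15 independent candidates* (half binary, half normal; 1,500 runs): mean OR when retained about 2.3 at 12% concordance and 1.9 at 25%; CI coverage when retained about 91%.
- *Three true ORs of 1.5 among 10 or 15 binary candidates* (latent correlation 0.2; 2,000 runs per setting; ORs averaged on the log scale):

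| Candidates | Concordance | Each true predictor retained | OR when retained | CI coverage when retained |
|---|---|---|---|---|
| 10 | 20% | 37.4% | 2.03 | 91.1% |
| 10 | 50% | 51.3% | 1.82 | 92.6% |
| 15 | 20% | 36.2% | 2.03 | 92.3% |
| 15 | 50% | 49.8% | 1.81 | 93.4% |

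**5. The alternative on the same simulated data.** With all 10 or 15 candidates kept in one pre-specified model, the mean OR is 1.52 to 1.53 and CI coverage is 94.4 to 94.8%.

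**6. Disagreement between the two caries models.** If a true predictor is retained with probability q in each model, and the two selections were independent, exactly one model keeps it with probability 2q(1−q): 2 × 0.36 × 0.64 = 46% and 2 × 0.51 × 0.49 = 50%. The same practitioners answer for both caries types, so the real figure should be lower. The calculation gives the scale, not a forecast.

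**The case against.** The strongest reply is that little depends on this model. It is labelled secondary. The primary analysis is descriptive, and Section 11.3 ties the decision on a future trial to willingness, recruitment ability and current use of selective removal. That stands, and it limits the weight of the point. The size of the bias also rests on inputs the protocol does not state, which stands too; only the direction is firm. It is not an answer that a statistical analysis plan may supply the detail. Such a plan could list the candidates and the alpha level, but the selection method itself is already fixed in the protocol.

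A reader might infer stronger versions that the document does not support:

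- **That stepwise selection creates a very high rate of false predictors.** With no true effects, at least one variable is retained in about 38% of simulated runs with 10 candidates and about 53% with 15. Plain multiplicity, 1 − 0.95^k, gives 40% and 54%. Each null variable is kept about 4% of the time. These rates come from examining many variables, and unadjusted ORs for the same variables would look nominally significant about as often.
- **That the CIs are badly too narrow.** For true predictors that are retained, the shortfall is mild. Coverage of 65 to 79% appears only when falsely retained terms are counted as well.
- **That Section 11.3 flatly contradicts Section 11.1.** Section 11.1 rules out formal testing for the study objectives, and Sections 3.1 and 3.2 do not list provider correlates among them. This is a wording conflict to reconcile.
- **That the candidate list is open or limited to enrollment-questionnaire items.** Section 11.3 says neither.
- **That about 46 events limit the model to 4 or 5 parameters.** The 12% behind that number is the share of general dentists using partial removal in a survey cited in Section 2.1. It is not a forecast at the 75% threshold. Section 2.2 reports that about half of dentists rejected evidence-based strategies, so far higher concordance is plausible; at 50% there would be about 192 events.

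**Conclusion.** The point holds as one about a fixed analysis method that does not suit its stated aim. With N = 385, 10 to 15 candidates, 0.05 at both steps and 12 to 50% concordance, a true OR of 1.5 would be reported as about 1.8 to 2.3 when retained, with CI coverage of about 91 to 93%. At 20 to 50% concordance, each such predictor would be retained in only about 36 to 51% of runs, so the symptomatic and asymptomatic models can differ by chance. The hand calculation gives nearly the same inflation (1.76 to 2.23) without simulation. The inflation is largest when concordance is low and moderate at 50%.

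The change should be made, but the point does not threaten the study's main results: the primary descriptive estimates and the inputs to the trial decision are unaffected.

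**What to change.** Replace the screening and stepwise text in Section 11.3 with one pre-specified multivariable logistic model, identical for symptomatic and asymptomatic caries.

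- **Contents.** Include practitioner age, gender and practice type. Section 2.2 already links age and gender to how invasively dentists treat deep lesions, and practice type is the sampling stratum. Add further named characteristics only as far as the observed number of events (or non-events, if fewer) allows. With practice type at four levels, the core model uses 1 + 1 + 3 = 5 parameters.
- **Reporting.** Give every OR with its 95% CI regardless of significance, and label the analysis exploratory. Show all other characteristics as unadjusted, descriptive ORs.
- **Consistency.** Reword Section 11.1 or 11.3 so that significance does not decide what is reported.

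The cost is analysis wording only: no change to the questionnaire, sampling or sample size. The downside is that characteristics outside the fixed list are reported unadjusted only.

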12 SOURCE DOCUMENTS AND ACCESS TO SOURCE DATA/DOCUMENTS

Source data/documents will be maintained by the NCC for this study. The NCC will program the electronic questionnaire into their EDC. Participants will be sent an email invitation with a direct link to the electronic questionnaire. After completion of the electronic questionnaire, data will be available through the EDC.

Only study personnel (i.e. NCC, PI and designated study team members) will have access to the data. All research computers and associated study documents will be password-protected and maintained in compliance with ICH E6, Section 4.9 and regulatory and institutional requirements for the protection of confidentiality of subjects. Study staff will permit authorized representatives of NIDCR and regulatory agencies to examine (and when required by applicable law, to copy) research records for the purposes of quality assurance reviews, audits, and evaluation of the study safety, progress and data validity.

The source documents for this study are:

- Electronic study questionnaire administered through the NCC EDC on the HUB website
- Data collected in the Network Enrollment Questionnaire

DCRS-Protocol-2021-02-22-V2.0 Page 21 of 29

13 QUALITY CONTROL AND QUALITY ASSURANCE

For the Quality Control (QC) and Quality Assurance (QA) activities associated with data collection and processing, the NCC will develop a Data Management Plan in which the specific data QC/QA procedures will be provided. These procedures will include the development of automatic data quality checks in the EDC for the questionnaire and the processes related to data accuracy and completeness. The EDC will be programmed with edit checks and response limiters to reduce data response errors.

DCRS-Protocol-2021-02-22-V2.0

14 ETHICS/PROTECTION OF HUMAN SUBJECTS

14.1 Ethical Standard

The PI and Co-Investigators will ensure that this study is conducted in full conformity with the principles set forth in The Belmont Report: Ethical Principles and Guidelines for the Protection of Human Subjects of Research, as drafted by the US National Commission for the Protection of Human Subjects of Biomedical and Behavioral Research (April 18, 1979) and codified in 45 CFR Part 46 and/or the ICH E6.

14.2 Institutional Review Board

The protocol, informed consent form(s), recruitment materials and all participant materials will be submitted to the Network's Central Institutional Review Board (IRB) for review and approval. The UAB IRB for Human Use serves as the Network's Central IRB. Approval of both the protocol and the consent form(s) must be obtained before any participant is enrolled. Any amendment to the protocol will require review and approval by the IRB before the changes are implemented in the study.

For those study investigators requiring IRB approval by their institutions, the study institution PI will submit for IRB approval and provide the Central IRB with the appropriate approved IRB documents.

14.3 Informed Consent Process

The standard waiver of documentation of signed informed consent for internet-based surveys will be requested for this study. Consistent with regulations outlined by the Central IRB, informed consent language will be provided on the entry page to the questionnaire and will indicate that consent is provided if the respondent chooses to enter the questionnaire via the link they have been provided (tacit consent).

14.4 Exclusion of Women, Minorities, and Specific Age Groups

Network dentists and dental therapists of any age, sex/gender or racial/ethnic group may participate if they meet the eligibility criteria.

14.5 Participant Confidentiality

Participant confidentiality is strictly held in trust by the investigators, study staff, and the study sponsor and their agents. The study protocol, documentation, data, and all other information generated will be held in strict confidence. No information concerning the study, or the data will be released to any unauthorized third party without prior written approval of the study sponsor.

Practitioners' pre-assigned identification numbers (PIDs) (practitioner IDs assigned by the Network) will be used to maintain study records and organize data files. A file linking participants' names with their unique identification number will be kept in a password-protected file by the NCC.

The study monitor or other authorized representatives of the NIDCR may inspect all study documents and records required to be maintained by the investigator.

The National Program Manager, who will be responsible for ensuring Network dentists completing the questionnaire are remunerated \$50, will be provided the minimum information necessary from the questionnaire to fulfill the responsibility of appropriately directing practitioner payments to their desired address.

Certificate of Confidentiality

To further protect the privacy of study participants, the Secretary, Health and Human Services (HHS), has issued a Certificate of Confidentiality (CoC) to all researchers engaged in biomedical, behavioral, clinical, or other human subjects research funded wholly or in part by the federal government. Recipients of NIH funding for human subjects research are required to protect identifiable research information from forced disclosure per the terms of the NIH Policy (https://humansubjects.nih.gov/coc/index). As set forth in 45 CFR Part 75.303(a) and NIHGPS Chapter 8.3, recipients conducting NIHsupported research covered by this Policy are required to establish and maintain effective internal controls (e.g., policies and procedures) that provide reasonable assurance that the award is managed in compliance with Federal statutes, regulations. and the terms and conditions of award. It is the NIH policy that investigators and others who have access to research records will not disclose identifying information except when the participant consents or in certain instances when federal, state, or local law or regulation requires disclosure. NIH expects investigators to inform research participants of the protections and the limits to protections provided by a Certificate issued by this Policy.

Confidentiality of Data Sharing

As described in section 16, it is NIH policy that the results and accomplishments of the activities that it funds should be made available to the public (see https://grants.nih.gov/policy/sharing.htm). PIs and funding recipient institutions will ensure that all mechanisms used to share data include proper plans and safeguards to protect the rights and privacy of individuals who participate in NIH-sponsored research.

15 DATA HANDLING AND RECORD KEEPING

The study team is responsible for ensuring the accuracy and completeness of the data reported, and for following the data collection procedures as outlined in the DMP. Access to study data will be provided to study team members by NCC staff.

15.1 Data Management Responsibilities

The PI will work closely with the NCC to ensure that the electronic surveys are collected appropriately and completely, and that confidentiality is being maintained according to protocol-specified procedures. Conference calls will be held approximately every month during the data collection phase to monitor progress, manage study documentation and procedures, and troubleshoot any problems.

The NCC will develop and maintain an EDC system including the study questionnaire. The DMP will include details on the EDC and procedures that will be followed to launch and monitor the study. The data reported in the Network's Practitioner Database will be used by the NCC to identify eligible dentists for this study.

15.2 Data Capture Methods

Data from the electronic questionnaire will be captured using REDCap forms in the EDC. The NCC will conduct preliminary testing and review of data fields in the initial programming and online launch of the questionnaire. The NCC will ensure that all required data are collected per protocol requirements and edit checks will be programmed in the web questionnaire to correct data issues in real time. The study team will ensure that data fields in the system are checked for completeness and accuracy so data entered in the EDC can be validated and data errors corrected in real time. Reports or tools will be developed to help monitor the data capture activities. The reports with the summary of data completeness and accuracy will be made available to the study team and NIDCR as requested.

15.3 Schedule and Content of Reports

Ongoing reports to monitor enrollment will be produced approximately monthly, or more frequently if desired, for study team and NIDCR review. The contents of the reports will include the summary of data collected and can be developed in separate sections by key characteristics or regions.

Final data analysis reports that address objectives of the study will be produced by the NCC for review by the study team and NIDCR. The content of these reports will be determined by the study team and the NCC and defined in the Statistical Analysis Standard Operating Procedure.

The procedure for locking the database prior to final analysis will be detailed in the study Data Management Plan. Briefly, the EDC data will be locked and final study datasets will be generated at the end of the study. Prior to locking the database, the NCC's Data Manager (DM) or designee will ensure all data are complete and clean as

DCRS-Protocol-2021-02-22-V2.0

determined by the study team. Then, the DM will obtain approval from the PI to proceed with the data lock.

No masking or coding is anticipated for this study.

15.4 Study Records Retention

Study records will be maintained for at least three years from the date that the grant federal financial report (FFR) is submitted to the NIH or longer as dictated by local IRB or state laws/regulations.

As outlined by IRB regulations, data will be destroyed in an appropriate and safe way. The file connecting subjects' names with their unique identification number will be kept in a password-protected file by the NCC and PI, in accordance with IRB regulations, before being securely erased on agreement by the ARC Director, the NCC Director and the PI.

15.5 Protocol Deviations

A protocol deviation (PD) is any change, divergence, or departure from the study procedures described in the IRB-approved clinical study protocol. The deviation may be on the part of the participant, the investigator, or study staff.

Consistent with the investigator obligations in the ICH E6 Guideline for Good Clinical Practice, the PI will document in study source documents and explain any deviation from the IRB-approved protocol. The PI will report to the IRB any deviations or changes made to eliminate immediate hazards to participants and any changes that increase risk to participants and/or significantly affect the conduct of the study.

Protocol deviations will be assessed for their impact on safety, study operations, and data integrity. Appropriate corrective and preventive actions will be implemented if warranted.

